6.0 Multiple sites: NA

7.0 Reliance Agreements/Single IRB: [name], [name], and [name] have Individual Investigator Reliance Agreements on this IRB.

[figure not shown]
8.0 Procedures Involved:

This study will use a parallel stratified randomized clinical trial design with repeated measures to examine the effects of a parent-implemented communication treatment (PICT) on parent use of communication support strategies and on pre-symbolic communicative acts and spoken language outcomes for children with HL. Children and their caregivers will be randomized to either PICT or a business-as-usual (BAU) control group. Children assigned to the PICT group will receive weekly, hour-long intervention sessions in their homes for 6 months. Parents and children will be assessed prior to intervention (at baseline, T0, pre), immediately after intervention (at T7, 7 months after baseline, post), 18 months after intervention (at T24, 24 months after baseline, follow-up), and monthly using abbreviated measures for the entire study (T0 – T24).

Parent-child dyads will be randomized individually following phone screening, completion of baseline assessments, and determination of hearing device status and communication mode. Randomization will be stratified by hearing device status (hearing aid or bone conduction device, cochlear implant) and communication mode (spoken only, sign + spoken). Given that hearing profiles will likely vary among participants, we chose to use hearing device as a stratification factor because it is categorical (hearing aid/bone conduction device or cochlear implant). Children who are a cochlear implant candidate will be assigned to the cochlear implant stratum. In addition, a child with one hearing aid and one cochlear implant will be assigned to the cochlear implant stratum.

Parents in both the intervention and BAU control groups will continue to receive early intervention services according to their individualized family service plan. Figure 2 illustrates the order of study procedures and stratification factors.

Page 4 of 20 Revised: May 25, 2018

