The child's SLP and/or DTH will be consented separately. They will each complete separate video-taped sessions up to 2 times over the course of the child's participation in the study – around month 4 and when the child is 30 months old. After each session, the therapist will be asked to complete surveys. If the child is not receiving speech or developmental services in the home, or if the therapist does not consent to this research, the child and parent can still participate in this research study.

Table 1. Summary of assessments

Assessment	Description	Participant	Duration	Location	Time Point
Communication and Symbolic Behavior Scales (CSBS)	The child is presented with toys and activities designed to elicit prelinguistic communication. The interaction is video recorded and then scored.	Parent and Child	30 min.	Home or Lab	Pre (T0) Post (T7)
Preschool Language Scale - Fifth Edition (PLS-5)	The child is presented with different receptive and expressive tasks such as following simple directions and labeling pictures until the child provides an incorrect response to six consecutive items for both auditory comprehension and expressive communication subscales	Child	30 min.	Home or Lab	Pre (T0) Post (T7) Follow- up (T24)
Language Sample	The child plays with four different sets of toys and looks at a wordless picture book, while the parent engages with the child but does not talk.	Child	12 min.	Home or Lab	Pre (T0) Monthly
Parent-Child Interaction	The child and parent play "as they usually would" with a set of toys for 12 minutes.	Parent and Child	12 min.	Home or Lab	Pre (T0) Monthly
TELE-ASD-PEDS	Virtual screening assessment for autism, Parents will be offered this assessment if the parent or the clinical team has concerns the child may have autism during the regular course of the study. Parents will also have the opportunity to consent to this assessment at 36-months.	Parent and Child	35-60 min.	Home	At parent request or with parent consent at 36- months

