Parent Surveys (for children with hearing loss)	The MacArthur-Bates Communicative Development Inventories (MCDI): Words and Gestures or Words and Sentences (the parent selects which words their child says and understands out of 680 words). English, Spanish, and American Sign Language versions (if applicable) Use of Community-Based Intervention Services and Hearing Device Log (the parent answers questions about how many and what types of other therapy services their child received in the last month; indicates how often the child wears their hearing device across 8 different routines, such as meal times)	Parent	Surveys (90 mins)	Home	Pre (T0) Post (T7) Follow-up (T24)
	LittlEars Auditory Questionnaire (the parent				

Page 6 of 20

Revised: May 25, 2018

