Parent Use of Communication Support Strategies	Latent	Parent use of communication support strategies coded from a parent-child interaction	The following measures from the coded parent-child interaction sample: Percentage of intervals in which the adult is	Monthly from 12 to 18 months of age (6 time points between pre and post)	Analysis 1.1: Dependent Analysis 2.1: Dependent Analysis 4.1a: Mediator Analysis 4.1b: Mediator
			communicating within the child's line of sight Percentage of adult communication that is paired with a gesture in the child's line of sight Percentage of intervals in which the adult's play is related and is in close proximity to the child Percentage of child nonverbal actions that are mirrored and mapped Percentage of child communication that is followed by a contingent response Percentage of adult communication that is in response to child communication Percentage of adult communication Percentage of adult communication that contains a child linguistic target Percentage of child communication to which the adult imitates and adds a word	Monthly from 18 to 36 months of age (18 time points between post and follow-up)	Analysis 3.1: Dependent Analysis 4.2a: Mediator Analysis 4.2b: Mediator
Child Prelinguistic Communicative Acts	Latent	Language Sample	Number of child prelinguistic communicative acts coded from the language sample	12 to 18 months of age (6 time points between pre and post)	 Analysis 1.2a: Dependent Analysis 2.2a: Dependent Analysis 2.3a: Dependent Analysis 4.1a: Dependent Analysis 4.3a: Mediator
Child Overall Prelinguistic Skills	Observed	Communication and Symbolic Behavior Scale (CSBS)	Total Scaled Score	At 18 months of age (post)	 Analysis 1.2b: Dependent Analysis 2.2b: Dependent Analysis 2.3b: Dependent Analysis 4.1b: Dependent Analysis 4.3a: Mediator Analysis 4.3b: Mediator
Child spoken words	Latent	MacArthur-Bates Communicative Development Inventory; Language Sample	Total number of Words Said from the MacArthur- Bates Communicative Development Inventory Total number of different spoken word roots from the language sample	18 to 36 months of age (18 time points between post and follow-up)	 Analysis 3.2a: Dependent Analysis 4.2a: Dependent Analysis 4.3a: Dependent
Child overall spoken language	Observed	Preschool Language Scale-5 th Edition	Total Standard Score	At 36 months of age (follow-up)	Analysis 3.2b: DependentAnalysis 4.2b: DependentAnalysis 4.3b: Dependent

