One example of a latent growth curve model is shown in Figure 2, where latent intercepts (level) and slopes (indicated by the circles labeled " L_c " and " S_c ") represent unmeasured variables that describe how children differ from each other in their overall level of prelinguistic development. These two latent variables predict and describe how children grow in their prelinguistic communicative abilities from age 12 months (C_{12}) to age 18 months (C_{18}). Latent growth models will be used for analyses 1.1 and 1.2a, all of which use a slope factor as a dependent variable.

Aim 1 analytic plan. Analyses for Aim 1 will utilize SEM equivalencies of both traditional regressions and growth curve extensions of these models. We will estimate all models in SEM to minimize the impact of attrition.

Analysis 1.1. Intervention will predict the slope factor in a latent growth curve model of overall parent use of communication support strategies, which is a latent variable of parent use of communication support strategies estimated monthly from 12 months (pre) to 18 months of age (post). This will utilize the CUFFS method (McArdle, 1988) of estimating growth in latent variables.

Analysis 1.2a. Intervention will predict the slope factor in a latent growth curve model of child prelinguistic communicative acts from a language sample from 12 months (pre) to 18 months of age (post). This will be accomplished by including intervention as a predictor in the child prelinguistic communicative acts growth curve.

Analysis 1.2b. CSBS Total Scaled Scores at 18 months of age (post) will be regressed on intervention status controlling for CSBS Total Scaled Scores at pre-test and other relevant covariates.

Aim 2 Analyses

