Analysis 2.3a. Intervention effects on a latent slope representing growth in child prelinguistic communicative acts from a monthly language sample from 12 months (pre) to 18 months of age (post) will be moderated by child attention to spoken language (orienting time toward speech from a sequential looking preference procedure) at 12 months of age (pre). Like analysis 2.2a, this model will be estimated using SEM due to the latent child growth outcome.

Analysis 2.3b. Intervention effects on observed CSBS Total Scaled scores at 18 months (post) will be moderated by child attention to spoken language (orienting time toward speech from a sequential looking preference procedure) at 12 months of age (pre). Like analysis 2.2b, this analysis will be carried out jointly using regression methods for assumption checking and SEM for robust estimation of final parameters.

Aim 3 Analyses

This aim tests the long-term effects of the intervention, both on parental use of communication support strategies and on child spoken language outcomes. We predict that: (a) parents in the intervention group will use more communication support strategies after intervention than parents in the control group (analysis 3.1); (b) children in the intervention group will have greater growth in spoken words between 18 months (post) and 36 months (follow-up) (analysis 3.2a) and greater overall spoken language outcomes at 36 months of age (follow-up) (analysis 3.2b) than children in the control group. As in Aim 1, we will employ a mix of traditional and advanced statistical methods, balancing simplicity of linear regression and related methods with sophisticated SEMs that handle attrition and missing data and allow for more flexible integration of time-varying covariates.

Aim 3 analytic plan. Analyses for Aim 3 will again utilize SEM for both regression and latent growth curve models, with the same benefits to attrition and estimation. The analyses here largely mirror those in Aim 1, looking at long-term rather than short-term intervention effects.

Analysis 3.1. Intervention will predict the slope factor in a latent growth curve model of overall parent use of communication support strategies, which is a latent variable of parent use of communication support strategies estimated monthly from 18 months (post) to 36 months of age (follow-up). This will utilize the CUFFS method⁸⁹ of estimating growth in latent variables.

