Analysis 3.2a. Intervention will predict the slope factor in a latent growth curve model of child spoken language outcomes (a latent variable of total number of different words said from the MCDI and total number of different spoken words from a language sample) from 18 months (post) to 36 months of age (follow-up). This will be accomplished by including intervention as a predictor in the child spoken word growth curve.

Analysis 3.2b. Intervention will predict PLS-5 Standard Scores at 36 months via multiple regression. We will test PLS-5 Standard Scores controlling for pre-test scores as we did in Analysis 1.2b.

Aim 4 Analyses

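### Analyses 3.1 and 3.2a do not commit to adjusting the T7–T24 growth curves for any pre-intervention value, although T0 values are collected; this gives up precision but does not bias the result

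*SAP*

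**What the plan says.** SAP Analysis 3.1 has intervention predict the slope of a latent parent-strategy variable "estimated monthly from 18 months (post) to 36 months of age (follow-up"). Analysis 3.2a does the same for spoken words over the same window: "This will be accomplished by including intervention as a predictor in the child spoken word growth curve". SAP Table 1 gives the occasions for child spoken words as "18 to 36 months of age (18 time points between post and follow-up"), and this one row serves every analysis in which the construct appears (3.2a, 4.2a, 4.3a).

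The pre-intervention data exist. Protocol section 8.0 schedules assessments at T0, T7 and T24 and "monthly using abbreviated measures for the entire study (T0 – T24"). Protocol Table 1 lists the language sample and the parent-child interaction at "Pre (T0) Monthly", and the parent surveys that contain the MCDI at "Pre (T0) Post (T7) Follow-up (T24"). The PLS-5 is also given at T0. Randomisation follows completion of the baseline assessments, so these values precede allocation.

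Elsewhere the SAP does use the pre-test. Analysis 1.2b is fitted "controlling for CSBS Total Scaled Scores at pre-test and other relevant covariates", and Analysis 3.2b, directly after 3.2a, states: "We will test PLS-5 Standard Scores controlling for pre-test scores as we did in Analysis 1.2b". The Aim 1 growth curves (1.1, 1.2a) begin at pre, so T0 is their first occasion.

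**The concern.** Among the Aim 1 and Aim 3 intervention-effect analyses, only 3.1 and 3.2a contain no stated pre-intervention value, either as an occasion or as a covariate. Their first modelled value is taken after six months of intervention. The T7 intercept cannot serve as a baseline, because treatment may already have moved it.

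The use of T0 differs between the two measures. T0 parent-strategy codes enter 1.1 but not 3.1. T0 spoken-word scores (MCDI words said, word roots from the language sample) enter no listed model.

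If children or parents who start higher also grow faster or slower after T7, part of the slope variance is predictable from T0. Leaving it in the residual widens the interval for the long-term effect, and any chance T0 difference between arms passes into the slope contrast unadjusted.

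**Working it through.** **1. Could another clause bring T0 in?**
- The SAP Covariates section lists cognition, hearing, device use, SES, language exposure and services. It does not list T0 values of parent strategies or spoken words, and its rule operates only when a group difference is found.
- The Missing data section adds predictors of missingness, drawn from the existing predictors and covariates.
- The Aim 3 analytic plan says its analyses largely mirror Aim 1. But the Aim 1 growth curves obtain T0 by starting there, and the Aim 3 curves start at T7.
- The Longitudinal mediation paragraph refers to relevant covariates in all analyses but names none.

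None of these commits to a T0 value.

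**2. The plan's own power figures.** Inputs from the SAP Power Analysis: N = 86 (96 less 10%), d = .61 at 80%, d = .71 at 90%, above 99% at d = 1.07; with N = 96, d = .58 and .67. Assumed: two-sided alpha .05 and 1:1 allocation. Method: two-sample noncentral t, df = N − 2, noncentrality d√(N/4).
- N = 86: 79.8% at .61, 90.2% at .71, 99.8% at 1.07.
- N = 96: 80.3% at .58, 90.1% at .67.

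The figures reproduce. The SAP says they assume pre-test control, but they match a pre-test correlation of zero, so they count no gain from baseline. The growth-model figures (d = .34 and .45) cannot be checked because the simulation inputs are not given. The d = .61 row is therefore used below only as a yardstick.

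**3. Gain from a T0 covariate.** Let r be the correlation of the T0 value with the child's T7–T24 slope. It is not in the documents, so a range is assumed. Slope variance removed is r²; interval width is multiplied by √(1 − r²); equivalent unadjusted N is 86/(1 − r²). Power uses d/√(1 − r²) with df = N − 3.

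| r | Variance removed | Width factor | Detectable d, 80% | Power at d = .61 | Equivalent N |
|---|---|---|---|---|---|
| 0 | 0% | 1.000 | .611 | 79.8% | 86 |
| .1 | 1% | .995 | .608 | 80.2% | 86.9 |
| .3 | 9% | .954 | .583 | 83.4% | 94.5 |
| .4 | 16% | .917 | .560 | 86.2% | 102.4 |
| .5 | 25% | .866 | .529 | 89.8% | 114.7 |

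These are upper limits, since they treat the slope as measured without error. In a 4,000-replicate simulation at r = .5 and d = .61, adjustment raised power from 79.6% to 89.5% with an error-free slope, and from 70.2% to 78.9% with slope reliability 0.8.

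**4. Chance imbalance.** With 43 per arm, the SD of the T0 difference is √(2/43) = 0.216 baseline SD, and the chance that it exceeds 0.2 SD in either direction is 35%. The shift in the slope contrast is r times the imbalance. At r = .4, a one-SD imbalance gives 0.216 × .4 = 0.086 SD. The mean absolute imbalance is 0.798 × 0.216 = 0.172, which gives 0.069 SD.

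**5. Validity without adjustment.** In the same simulation, the unadjusted and adjusted contrasts both averaged the true effect, and type I error stayed near 5% for both (4.2% to 5.3% across settings).

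**The case against.** The strongest reply is that nothing here is invalid. A randomised comparison of slopes is unbiased without covariates, and its standard error already includes the variability from chance imbalance. Lost precision and unadjusted imbalance are therefore one cost seen from two sides, not two harms. This stands.

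Second, r may be small. The outcome is a slope, so T0 level matters only if it predicts later growth. If T0 word counts at 12 to 18 months are near floor, r for words could be about .1 and the gain almost nothing. This also stands. It is why the range must include .1, and why the PLS-5 is proposed beside the word count.

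Third, the SAP's general covariate wording leaves room for T0 adjustment, and the sentence in 3.2a does not say that intervention is the sole predictor. That is right: the gap is a missing commitment. But an open choice of covariate can be made after the data are seen, and 3.2b shows that the authors state pre-test control where they intend it.

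A reader might infer more than this:
- That the long-term effect is biased or type I error inflated. Randomisation and the simulation say otherwise.
- That the T0 data are wasted altogether. T0 parent codes are used in 1.1, 2.1 and the 4.1 analyses, and the T0 language sample in 1.2a and others. Only the T0 spoken-word scores go unused.
- That the SAP decided to exclude T0. No passage says so.

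**Conclusion.** The point holds as a free improvement in precision and prespecification. Analyses 3.1 and 3.2a leave adjustment for a pre-intervention value unstated, out of line with 3.2b. Validity is not in question.

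The size depends on a correlation that the documents do not give: from negligible at r = .1 (detectable d moves from .611 to .608) to worthwhile at r = .5 (.611 to .529, or power at d = .61 from 79.8% to 89.8%), less where slopes are measured with error. These figures assume 1:1 allocation, two-sided alpha .05, N = 86 and a simple two-sample comparison of slopes. They show scale and do not recalculate the plan's growth-model power.

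**What to change.** Add one sentence to each analysis.
- **3.1:** regress the intercept and slope factors on an observed composite of the T0 parent-strategy codes, with the composite defined in the SAP. An observed score avoids adding a T0 measurement model.
- **3.2a:** regress the intercept and slope factors on a fixed T0 set: MCDI words said and the PLS-5 score already used as the pre-test in 3.2b. Using both from the start covers the case where T0 word counts are near floor.

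State that these covariates enter whether or not the arms differ at T0, and that the set will not be changed after T0 data are inspected. The cost is one extra parameter per growth factor in 3.1 and two in 3.2a. No new data are needed.

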Multicollinearity. This proposal includes a large set of prelinguistic and linguistic variables, some of which will be included in the same analyses. Our data reduction is one part of our solution to multicollinearity, such that latent constructs that account for shared variation between comparable predictors will be used when possible. In other cases, we will control for multiple collinear variables in the same analysis, specifically when using multiple coded variables from naturalistic parent-child interactions. In those cases, we will use alternative decomposition and transformation methods. Principle components analysis (PCA) can transform a set of collinear predictors into a set of uncorrelated variables representing variance in the original data. For example, a simple PCA of one parent and one child variable would yield two components: one indicating shared family level behavior and the other representing scaled differences between parent and child. We will further explore non-linear transformations to make sure non-linear associations and distributional assumptions are accounted for, including both simple (e.g., polynomial or logarithmic transformations to improve distributions) and complex (e.g., adjusting observed child communication for proportion of time spent communicating) transformations. This set of methods integrates well within our SEM framework and multivariate longitudinal design.

Missing data. Given this is an intent-to-treat trial, all 96 children randomized will be included in the analyses of primary outcomes even if data are missing. However, our preliminary studies showed high retention rates (e.g., 95% retention in the pilot study - R03DC012639), but missing data occurs in all longitudinal studies. All models will be estimated using full information maximum likelihood (FIML), which uses all available data and yields unbiased parameter estimates under the most common missingness mechanisms. We will further use our set of predictors and covariates to predict missingness, and include those variables as covariates to conform to FIML assumptions. For non-ignorable missing data, we will conduct sensitivity analyses using non-ignorable pattern-mixture and selection models to investigate the robustness of our conclusions across the different models for missing data.

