Power for tests of intervention effects were estimated using G*Power⁹⁵ supplemented with custom simulations to verify accuracy and tailor assumptions to our research design. Given a sample size of 86 (96 recruited participants with 10% attrition), we project greater than 99% power for main effects of the intervention (aim 1) as large as those shown in our pilot study (d=1.07) (see Justification and Feasibility in Research Strategy). We further project 80% power for effects as low as d=.61 and 90% for d=.71. Each of the three previous estimates assume control for pre-test and 10% attrition (e.g., n=86). Our research group has maintained greater than 95% retention in comparable studies over the last two years. We would retain power for smaller effect sizes of d=.58 (80% power, down from d=.61) and d=.67 (90% power, down from d=.71) if no attrition occurs.

The above power analysis covers the primary analyses for Aims 1 and 3. However, these aims also include growth in parent and child outcomes assessed monthly. These analyses depend on latent growth curve models, as described above and require a simulation-based power estimate, as described in Zhang & Wang (2009). We simulated our monthly assessments four thousand times, varying our predicted effect size and distribution of latent intercepts and slopes. This simulation yielded reliable power estimates for each effect size. The use of longitudinal data yield improved power over our simple pre-test-post-test designs in the previous paragraph. We project 80% power for d=.34, and 90% for d=.45. Furthermore, we have 80% power to detect moderators (aim 2) that account for 7.8% of variance in the outcome or greater, and 90% for 10.4% of variance. In summary, this study is well-powered to test the effects of intervention on parent and child outcomes.

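### Analysis 3.2b leaves the T7 PLS-5 out of the model, so FIML recovers nothing for a child without a T24 score, and the missing-data wording would allow that score to enter in the wrong role.

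*SAP*

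**What the plan says.** Analysis 3.2b (SAP, Aim 3) regresses the 36-month PLS-5 on intervention: "We will test PLS-5 Standard Scores controlling for pre-test scores as we did in Analysis 1.2b". The analysis it refers to reads: "CSBS Total Scaled Scores at 18 months of age (post) will be regressed on intervention status controlling for CSBS Total Scaled Scores at pre-test", with room for other relevant covariates. SAP Table 1 takes the PLS-5 at follow-up only. The protocol's assessment table (section 8.0, Table 1) lists it at "Pre (T0) Post (T7) Follow- up (T24"), so a T7 score on the same instrument exists and no named SAP analysis uses it.

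On attrition, the SAP Overview says that fitting every model as an SEM keeps the same full sample throughout. The Missing data paragraph says all 96 randomized children are included in the primary-outcome analyses, with FIML as estimator. It then adds: "We will further use our set of predictors and covariates to predict missingness, and include those variables as covariates to conform to FIML assumptions". It also plans pattern-mixture and selection models as sensitivity analyses for non-ignorable missingness. The Power Analysis, however, counts completers only: "Given a sample size of 86 (96 recruited participants with 10% attrition), we project greater than 99% power for main effects of the intervention".

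**The concern.** FIML uses whatever variables are in the model, and only those. With a single outcome, a child who leaves between T7 and T24 has nothing in the model that carries information about the T24 score beyond arm and pre-test. The T7 PLS-5, probably the best available predictor of the missing value, stays outside. The protection against attrition that the SAP attributes to SEM is therefore absent from this analysis.

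The sentence on predictors of missingness does not close the gap safely. It gives them the role of covariates and does not confine them to baseline. The Covariates paragraph also admits any listed variable on which the arms differ at any time in the study. A T7 score lies on the path from treatment to the T24 outcome. Conditioning on it removes the part of the effect already present at T7. At stake is the estimate of the long-term effect on spoken language, if withdrawal over the 17 months from T7 to T24 is related to progress at T7 and that relation differs by arm.

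**Working it through.** **Plan's own figures.** Two-sample t-test, two-sided 0.05, 1:1 (level, sidedness and allocation are assumed; the SAP gives none). For n=86, non-centrality is d × √(43/2) = 0.61 × 4.637 = 2.83, and power is 0.798. At d=0.71 it is 0.902. This reproduces "We further project 80% power for effects as low as d=.61 and 90% for d=.71". With 48 per arm, d=0.58 gives 0.803 and d=0.67 gives 0.901, reproducing "smaller effect sizes of d=.58 (80% power, down from d=.61) and d=.67 (90% power, down from d=.71) if no attrition occurs". So the power section already treats a child without an end score as lost.

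**FIML against complete cases.** The likelihood splits into f(T0 | arm) × f(T24 | arm, T0). A child without T24 enters only the first factor, which shares no parameter with the arm effect on T24. A direct check on one simulated trial with 82 of 96 end scores seen gave 0.61847 by FIML and 0.61847 by complete-case regression.

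**Joint model.** With T7 as a second outcome and monotone loss after T7, the maximum-likelihood arm effect at T24 is b_arm + b_T7 × a_arm. Here a_arm is the arm effect on T7 (given T0) in all children, and the b terms come from regressing T24 on arm, T0 and T7 in completers.

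**T7 as covariate.** This reports b_arm alone. With equal residual SDs, an assumed effect of 0.60 at both times and residual correlation ρ, b_arm = 0.60 × (1 − ρ). That is 0.30 at ρ=0.5 and 0.18 at ρ=0.7.

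**Bias of the planned model.** It is roughly ρ × (shift in mean T7 residual among PICT completers − the same shift among control completers). Equal shifts cancel. Simulation used 48 per arm, pre-test correlation 0.5, true effect 0.60, ρ from 0.5 to 0.7, and informative loss with dropout odds changing about 7-fold per SD of T7:

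| Withdrawal after T7 | 3.2b as written | T7 and T24 jointly |
|---|---|---|
| Random, 5 of 48 per arm | 0.60 | 0.60 |
| Low scorers, equally from both arms, 5 of 48 | 0.60 | 0.60 |
| Low scorers from control, random from PICT, 5 of 48 | 0.54–0.51 | 0.60 |
| Low scorers from control, high scorers from PICT, 5 of 48 | 0.48–0.43 | 0.60 |
| Either of the last two patterns, 2 of 48 per arm | 0.58–0.53 | 0.60 |

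At 10% loss the bias is 0.06 to 0.17, against a standard error of about 0.187, so 0.3 to 0.9 standard errors. A separate simulation with true effect 0.61 and T7–T24 correlation 0.6 to 0.8 gave 0.46–0.55 as planned when loss differed by arm, and about 0.61 jointly. It also applied one T7-dependent dropout rule to both arms and obtained 0.56–0.60. This need not contradict the second row of the table, where the same number leaves each arm: if the arms differ at T7, a common rule on the raw score can remove more children from the lower-scoring arm.

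**Precision.** 1/N_eff = (1 − ρ²)/86 + ρ²/96, if all ten lost children have a T7 score. At ρ=0.5: 0.75/86 + 0.25/96 = 0.01133, so N_eff = 88. At ρ=0.9, N_eff = 94. The effect detectable at 80% power moves from 0.61 to between 0.60 and 0.58. Under random loss the simulated standard error falls from 0.187 to 0.185 (ρ=0.5) or 0.181 (ρ=0.7).

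**The case against.** ANCOVA on a single end score is a standard primary analysis, and several features of the plan limit the damage.

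A reader might infer that the SAP's only remedy for missing data would adjust away the effect. The documents do not support that. Pattern-mixture and selection models are also planned. The listed covariates (cognition, hearing, device use, SES, language exposure, services) include neither the T7 PLS-5 nor any monthly language score. The 0.30–0.18 figure describes an analysis the wording permits but does not propose. What stands is that the covariate step is the only one stated under missing-at-random and does not exclude post-randomisation variables.

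A reader might also infer that 3.2b is biased as written. That requires T7-dependent withdrawal to differ by arm, and the documents give no reason to expect it. Control families keep their early-intervention services (Protocol 8.0). PICT lasts six months, so neither arm has study sessions between T7 and T24. Visits, payments and the tablet incentive are the same. Retention above 95% is reported for comparable studies. All of this makes a large bias less likely without ruling out a smaller one.

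Nor do withdrawn families add nothing to the trial: their monthly data count in growth curves such as 3.2a, and a family leaving after T7 counts fully in 1.2b. The exploratory Analyses 4.2b and 4.3b also place monthly measures beside the T24 PLS-5. None of this changes the arm effect tested in 3.2b. Finally, extending the point to 1.2b at equal strength is not justified, because there is no intermediate CSBS and the gain from monthly counts has not been quantified.

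**Conclusion.** The point holds for Analysis 3.2b. For its arm effect, FIML on the stated model is complete-case analysis, so the full-sample claim has no force there for children without a T24 score. That part is algebra and needs no assumption about dropout, given fully observed predictors.

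The consequence is conditional. If withdrawal is random, or removes low scorers equally from both arms, there is no bias and the joint model buys only a little precision. If T7-dependent withdrawal differs by arm, the loss at 10% attrition is about 0.06 to 0.17 SD of an assumed 0.60, and less at the retention the sponsor reports. Entering T7 PLS-5 as a covariate would cost more than leaving it out, by an amount that depends on the effect at T7 and the correlation. All sizes rest on assumed correlations, T7 effects and dropout mechanisms. The change is worth making because it is cheap and uses data already collected; the analysis is not invalid without it.

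**What to change.** - In 3.2b, fit T7 and T24 PLS-5 jointly. Regress each on arm and T0 PLS-5, let the residuals correlate, and test the arm effect on T24. The target remains the T24 difference between arms.
- In the Missing data paragraph, state that only baseline predictors of missingness enter as covariates, and that post-randomisation predictors enter as auxiliary variables.
- In 1.2b, a small summary of the monthly prelinguistic-act counts may be added as an auxiliary variable in the same way. Its benefit is not quantified here.
- Keep the pattern-mixture and selection models as sensitivity analyses.

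The cost is SAP wording and a few extra model parameters, with no new data, visits or participants. The joint model helps only children who reach T7. If analysis by arm has already begun, report it as a labelled sensitivity analysis beside 3.2b as planned.
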